IPD	important protocol deviation
IRB	institutional review board
IWRS	interactive web response system
LN	levonorgestrel
MedDRA	Medical Dictionary for Regulatory Activities
NA	not applicable
PC	publication committee
PD	Pharmacodynamics
PE	physical examination
P-gp	P-glycoprotein
PI	principal investigator
PK	pharmacokinetic, pharmacokinetics
PR	PR interval, segment
PRO	patient-reported outcome
PT	Preferred Term
QRS	the portion of an ECG comprising the Q, R, and S waves, together representing ventricular depolarization
QT	QT interval
QTcF	QT interval corrected by Fridericia's formula
RR	interval from the onset of 1 QRS complex to the next
SAE	serious adverse event
SAP	statistical analysis plan
SC	steering committee
SD	standard deviation
SF-36	Short Form Health Survey 36
SFUV	Safety Follow-up Visit
SGLT2	sodium-glucose co-transporter-2
SI	SI units (International System of Units)
SOC	System Organ Class
SRA	serum resistant associated-protein
SUSARs	suspected, unexpected, serious adverse reactions
TE	Treatment-emergent
TEAE	treatment-emergent adverse event
UACR	urine albumin to creatinine ratio
ULN	upper limit of normal

Abbreviation	Definition
UPCR	urine protein to creatinine ratio
V _{ss} /F	apparent volume of distribution at steady-state
WHO-DD	World Health Organization-Drug Dictionary

5 INTRODUCTION

5.1 FSGS Background

Focal segmental glomerulosclerosis (FSGS) is a rare kidney disease with an estimated global incidence of 0.2 to 1.1/100,000/year.¹ FSGS is caused by damage to podocytes, which are part of the glomerular filtration barrier, resulting in proteinuria.² Patients with nephrotic-range proteinuria (i.e., protein to creatinine ratio >3 g/g) are at a higher risk of developing end-stage kidney disease (ESKD) and developing proteinuria-related complications, such as infections or thromboembolic events. There is no well-standardized treatment regimen for FSGS. Current therapeutic options for patients with FSGS who have nephrotic-range proteinuria include high-dose corticosteroids, which induce remission of proteinuria in a minority of patients.²

FSGS can be divided into different subgroups based on the underlying etiology. One homogeneous subgroup of FSGS is characterized by the presence of 2 independent common sequence variants in the apolipoprotein L1 (*APOL1*) gene termed *G1* and *G2*, which are referred to as the "*APOL1* risk alleles." *G1* encodes a correlated pair of non-synonymous amino acid changes (S342G and I384M), *G2* encodes a 2 amino acid deletion (N388del:Y389del) near the C-terminus of the protein, and *G0* is the ancestral (low risk) allele.^{3,4}

The APOL1 gene is expressed in multiple organs in humans, including the liver and kidney.^{5,6} The biologic function of APOL1 is to protect against parasitic infection (*Trypanosoma brucei brucei [T. b. brucei]*).⁷ APOL1 is endocytosed by *T. b. brucei* and transported to lysosomes, where it inserts into the lysosomal membrane and forms pores that lead to parasite swelling and death.⁸ While the ability to lyse *T. b. brucei* is shared by all 3 APOL1 variants (*G0*, *G1*, and *G2*), APOL1 *G1* and *G2* variants confer additional protection against parasite species that have evolved a serum resistant associated-protein (SRA) which inhibits APOL1 *G0*; these species cause sleeping sickness. *G1* and *G2* variants evade inhibition by SRA and *G1* confers additional protection against *T. b. gambiense* (which causes West African sleeping sickness), and *G2* confers additional protection against *T. b. rhodesiense* (which causes East African sleeping sickness).⁹

In the kidney, APOL1 is expressed in podocytes, endothelial cells (including glomerular endothelial cells), and some tubular cells.^{6, 10} Podocyte-specific expression of *APOL1 G1* or *G2* (but not *G0*) in transgenic mice induces structural and functional changes, including albuminuria, decreased kidney function, podocyte abnormalities, and glomerulosclerosis.¹¹ Consistent with these data, *G1* and *G2* variants of *APOL1* play a causative role in inducing FSGS and accelerating its progression in humans. Individuals with 2 *APOL1* risk alleles (i.e., homozygous or compound heterozygous for the *APOL1 G1* or *APOL1 G2* alleles) have increased risk of developing FSGS with an odds ratio of 10 to 17, and they are at risk for rapid decline in kidney function if they develop FSGS.^{3, 4, 12} Thus, inhibition of APOL1 could have a positive impact in individuals who harbor 2 *APOL1* risk alleles.

This study is a Phase 2a proof-of-concept study designed to assess the efficacy effects, safety, and pharmacokinetics (PK) of VX-147 in subjects with APOL1-mediated FSGS.

5.2 VX-147 Background

VX-147 is a small molecule that inhibits APOL1-induced cell death and inhibits the biological function of APOL1, i.e., APOL1-induced lysis of *T. b. brucei*. These nonclinical data suggest that VX-147 has the potential to reduce proteinuria and reverse APOL1-induced podocyte

lesions in patients with APOL1-mediated FSGS. Therefore, VX-147 is being developed to treat individuals with FSGS who also have 2 *APOL1* risk alleles and nephrotic-range proteinuria.

In vitro studies indicated VX-147 is a weak inducer of CYP3A4; however, in a previous clinical study (VX18-147-001; Study 001) an interaction with midazolam, a sensitive substrate of CY3A4, indicated that VX-147 has minimal inhibitory effect. To characterize the CYP3A4mediated PK interaction between VX-147 and combined oral contraceptives containing the steroids, ethinyl estradiol (EE, 30 µg)/levonorgestrel (LN, 150 µg), a dedicated drug-drug interaction (DDI) study was conducted, Study VX19-147-004 (Study 004; analysis complete; CSR in preparation). The effect of multiple doses of 45 mg VX-147 was assessed on the steadystate PK of LN and EE. The study design was an open label, 2-period, fixed-sequence crossover study in 17 healthy female adult subjects. Steady-state plasma levels of EE and LN did not decrease in the presence of daily doses of 45 mg VX-147. There were minor (~20%) increases in AUC_{0-24h,ss} of both EE and LN. Geometric mean ratio (GMR) of AUC_{0-24h} for EE at steady state was 1.20 (90% confidence interval [CI] of 1.14, 1.27) and that for LN was 1.20 (1.14, 1.27). The steady state C_{max} of EE and LN also increased with a GMR (90% CI) of 1.23 (1.10, 1.38) for EE and 1.08 (1.00, 1.17) for LN. VX-147 was safe and well tolerated in this study, and there were no discontinuations. There were no serious adverse events (SAEs), and all AEs were mild in severity. Based on these results the magnitude of these interactions are not deemed clinically significant; therefore, coadministration of VX-147 and combined oral contraceptives containing EE and LN is unlikely to result in contraceptive failure.

There were no serious adverse events (SAEs), and all AEs were mild or moderate in severity. Two subjects discontinued due to AEs. Of these, one subject (60 mg qd or placebo) discontinued on Day 7 due to a mild AE of tachycardia and another subject (90 mg qd or placebo) discontinued due to a moderate AE of COVID-19 infection. Both were reported by the investigator to be not related.

In Study 008, the highest dose of 120 mg qd for 14 days was generally safe and well tolerated. Preliminary PK analysis demonstrated that the mean (CV%) $AUC_{0-24h,ss}$ achieved at this dose was 50.1 (27.5%) μ g*h/mL, providing an approximately 3.8-fold exposure margin over the 45 mg qd clinical dose with a mean (CV%) $AUC_{0-24h,ss}$ of 13.3 (21.5%) μ g*h/mL (Study 001). A moderate CYP3A4 inhibitor, such as cyclosporine, is expected to result in a less than 2-fold increase in $AUC_{0-24h,ss}$.

Additional information about the first-in-human (FIH) study (Study 001) and nonclinical studies is available in the Investigator's Brochure.

6 STUDY OBJECTIVES

6.1 Part A (Treatment Period)

6.1.1 Primary Objective

• To evaluate the ability of VX-147 to reduce proteinuria

6.1.2 Secondary Objectives

- To evaluate the safety and tolerability of VX-147
- To characterize the PK of VX-147

6.2 Part B

6.2.1 Exploratory Objective

• To evaluate the change proteinuria after stopping administration of VX-147

7 STUDY ENDPOINTS

7.1 Part A

7.1.1 Primary Endpoints

• Percent change from baseline in urine protein to creatinine ratio (UPCR) at Week 13

7.1.2 Secondary Endpoints

- Safety and tolerability based on adverse events (AEs), clinical laboratory values (i.e., hematology, serum chemistry, urinalysis, coagulation studies), standard 12-lead ECGs, and vital signs
- Plasma PK of VX-147

7.1.3 Exploratory Endpoints

Percent change from baseline in UPCR over time during the Treatment Period

- Percent change from baseline in urine albumin to creatinine ratio (UACR) at Week 13
- Percent change from baseline in UACR over time during the Treatment Period
- Change from baseline in patient-reported outcome (PRO) Short Form Health Survey 36 (SF-36) over time during the treatment period
- Change from baseline in SF-36 at 4 weeks after the last dose (Safety Follow-up Visit [SFUV])

7.2 Part B (Optional Off-treatment Follow-up Period)

7.2.1 Exploratory Endpoints

• Percent change from baseline in UPCR at the end of the Off-treatment Follow-up Period

8 STUDY POPULATION

Eligibility will be reviewed and documented by an appropriately qualified member of the investigator's team before subjects are enrolled.

Subjects who meet all of the inclusion criteria and none of the exclusion criteria will be eligible.

8.1 Inclusion Criteria

The following criteria are applicable for Cohort 1 and Cohort 2:

- 1. Willing to sign and date an informed consent form (ICF).
- 2. Willing and able to comply with scheduled visits, treatment plan, study restrictions (Section 9.59.4), laboratory tests, contraceptive guidelines (Section 11.6.5), and other study procedures.
- 3. An *APOL1* genotype of *G1/G1*, *G2/G2*, or *G1/G2* obtained with a Vertex-approved clinical study assay.
- 4. Between the ages of 18 and 65 years, inclusive.
- 5. Body mass index (BMI) of 18.0 to 40.0 kg/m², inclusive, and a total body weight >50 kg.
- 6. FSGS diagnosed by kidney biopsy, with the exception of the tip variant, as confirmed through the eligibility review process.
- 7. There should be no plan to start, stop, or modify dosing for an angiotensin converting enzyme (ACE) inhibitor, angiotensin receptor blocker (ARB), neprilysin inhibitor, sodium-glucose co-transporter-2 (SGLT2) inhibitor, renin inhibitor, systemic corticosteroids, tacrolimus, mycophenolate, or cyclosporine from 28 days before Screening through the Follow-up Period.
- 8. Subjects who are on low-dose corticosteroids (prednisone ≤ 10 mg per day or prednisone equivalent) or on an allowed immunosuppressant (i.e. tacrolimus, mycophenolate, or cyclosporine) must be on a stable dose for 28 days before screening.
- 9. Estimated glomerular filtration rate (eGFR) ≥30 mL/min/1.73 m² (±10%) based on the Chronic Kidney Disease Epidemiology Collaboration (CKD-EPI) equation. ^{13, 14}

10. Subjects with eGFR \geq 30 (\pm 10%) to \leq 40 mL/min/1.73 m² must have tubulointerstitial fibrosis \leq 50% or described as no, mild, or moderate on their kidney biopsy.

The following criterion is applicable for Cohort 1:

11. A UPCR ratio of ≥ 3 g/g ($\pm 10\%$) and ≤ 10 g/g in the first morning void on 3 measurements collected on at least 3 separate days within a 7-day period, during the Screening Period. The average of the 3 measurements must meet this criterion.

The following criterion is applicable for Cohort 2:

12. A UPCR ratio of ≥0.8 g/g (±10%) and <2.7 g/g in the first morning void on 3 measurements collected on at least 3 separate days within a 7-day period, during the Screening Period. The average of the 3 measurements must meet this criterion.

8.2 Exclusion Criteria

The following criteria are applicable for Cohort 1 and Cohort 2:

- 1. History of any illness or any clinical condition that, in the opinion of the investigator, might confound the results of the study or pose an additional risk in administering study drug(s) to the subject. This includes, but is not limited to, the following:
- Solid organ or bone marrow transplantation
- Cancer, except for squamous cell skin cancer, basal cell skin cancer, and Stage 0 cervical carcinoma in situ
- Clinically significant and active bacterial, viral, fungal, or parasitic infection as determined by the investigator
- Clinically significant liver disease
- Ongoing alcohol or drug abuse as determined by the investigator
- Any condition possibly affecting drug absorption (e.g., gastrectomy, gastrointestinal tract surgery except appendectomy and cholecystectomy)
- Stroke or myocardial infarction within 6 months before Day 1
- 2. Evidence of non-APOL1-mediated FSGS. This includes but is not limited to the following:
- FSGS occurring concomitantly to administration of drugs known to induce FSGS, including but not limited to lithium, interferon, and bisphosphonates (e.g., pamidronate), or FSGS occurring in a subject using intravenous illicit drugs at the time of diagnosis.
- Evidence of another underlying kidney disease that can cause FSGS, including evidence of
 congenital anomaly of the kidney or urinary tract (CAKUT) on renal ultrasound, history of
 CAKUT, history of nephrectomy.
- FSGS occurring in a subject with known sickle cell disease.
- Known genetic mutation other than APOL1 G1 or G2 that is associated with FSGS.
- Positive serology for human immunodeficiency virus-1 (HIV-1) or human immunodeficiency virus-2 (HIV-2).

- 3. Evidence of kidney disease other than FSGS on kidney biopsy, as assessed by the eligibility review process.
- 4. Kidney biopsy showing the tip variant of FSGS, as assessed by the eligibility review process.
- 5. Abnormal laboratory values at screening that present a risk to subject safety in the opinion of the investigator, or any of the following abnormal laboratory values at screening:
- Total bilirubin $\geq 1.5 \times$ upper limit of normal (ULN)
- Aspartate transaminase (AST) or alanine transaminase (ALT) $\ge 2 \times ULN$
- Serum albumin <1 g/dL
 - Hemoglobin <10 g/dL.
- 6. Positive for hepatitis B surface antigen (HBsAg) or hepatitis C virus (HCV) nucleic acid during screening.
- 7. Risk factors for Torsade de Pointes (e.g., familial long QT syndrome, chronic hypokalemia, heart failure) or concomitant medications that prolong the QT/QTc interval or any history of cardiac disorders that, in the opinion of the investigator, might put the subject at risk or may confound the results of the study.
- 8. Any clinically significant ECG abnormality (as determined by the investigator) or median QTcF of triplicate standard 12 ECGs >450 msec at screening.
- 9. Screening blood pressure ≥160 mm Hg (systolic) or ≥100 mm Hg (diastolic), based on the average of 3 measurements.
- 10. Pregnant or nursing female subjects.
- 11. Subjects of reproductive potential who are not willing to follow the contraception requirements outlined in Section 11.6.5.1.
- 12. Plan to travel to countries where sleeping sickness is endemic, from the Screening Visit through 1 week after the last dose of study drug.
- 13. Subject, or close relative of the subject, is the investigator or a subinvestigator, research assistant, pharmacist, study coordinator, or other staff directly involved with the conduct of the study at that site.
- 14. Hypersensitivity to investigational medicinal product or to any of its excipients.
- 15. Use of the substances or activities as indicated in Section 9.5 during the specified times, including but not limited to ongoing treatment with high doses of corticosteroids (>10 mg/day of prednisone or prednisone equivalent) or an immunosuppressive drug other than tacrolimus, mycophenolate, or cyclosporine.

9 STUDY IMPLEMENTATION

9.1 Study Design

This is a single-arm, open-label, 2-part study. In Part A, all subjects will receive VX-147 at a dosage of 15 mg qd for 2 weeks and VX-147 at a dosage of 45 mg qd for 11 weeks. Part A will be enrolled in 2 cohorts: Cohort 1 and an optional Cohort 2. Cohort 1 includes up to 10 subjects

with UPCR approximately \geq 3 g/g and < 10 g/g and eGFR approximately \geq 30 mL/min/1.73 m². Optional Cohort 2 includes approximately 10 subjects with UPCR approximately \geq 0.8 g/g and <2.7 g/g and eGFR approximately \geq 30 mL/min/1.73 m².

[figure not shown]
Subjects in Cohort 1 and Cohort 2 are permitted to take a stable low dose of systemic corticosteroid (prednisone ≤ 10 mg per day or prednisone equivalent) and/or an allowed immunosuppressant (i.e., tacrolimus, mycophenolate, or cyclosporine).

Enrollment of Cohort 1 and Cohort 2 will be managed through the interactive web response system (IWRS).

In Optional Part B, subjects will be followed for up to 12 weeks for evaluation of proteinuria off-treatment (Section 9.1.3).

All subjects will complete a SFUV at 28 (\pm 7) days after the last dose of study drug.

Figure 9-1 VX19-147-101 Study Design

D: Day; PK: pharmacokinetics; qd: once daily; UPCR: urine protein to creatinine ratio; W: Week Notes: The figure is not drawn to scale. After completing Part A, subjects will be followed monthly for up to 12 weeks or until UPCR returns to baseline, whichever occurs first. All subjects will be required to complete a SFUV at 28 (± 7) days after the last dose of study drug.

Proteinuria will be assessed at multiple timepoints throughout the Treatment Period and Off-treatment Follow-up. Triangles represent timepoints for the primary analysis.

9.1.1 Screening

Screening Visit assessments are listed in Table 3-1. Subjects may choose to complete all screening assessments within the 28-day Screening Period or they may choose a 2-step screening process and first complete only the *APOL1* genotype assessment at any time before Day -1 (including before Day -28), followed by the rest of the screening assessments during the 28-day Screening Period. The ICF will outline the screening options. *APOL1* genotype results must be obtained using a Vertex-approved clinical study assay. If genotype results are available in the medical records and a Vertex-approved clinical study assay was used, the genotype assessment does not need to be done.

With the exception of genotyping, all screening assessments will occur within 28 days before administration of study drug. The investigator (or an appropriate authorized designee at the study site) will obtain informed consent in person or remotely (Section 13.2.2) from each subject before conducting any study-related procedure.

The Screening Visit and informed consent should occur in the clinic if possible. If the subject is unable or unwilling to visit the clinic for screening due to extenuating circumstances, the Screening visit may occur using a home health nurse. Remote informed consent may be obtained before the home health visit.

To prepare for study participation, subjects will be instructed on the study restrictions (Section 9.5).

9.1.1.1 Repetition of Screening Assessments

Screening assessments may be repeated once per screening to establish study eligibility. If repeat values of the individual assessment(s) are within the eligibility criteria and completed within the screening window, then the subject is eligible for the study.

Additional repetition of any individual screening assessment that did not meet eligibility criteria is not permitted, unless there is clear evidence of a laboratory error (e.g., hemolysis of sample) or equipment failure, or if the investigator believes the result is not consistent with the subject's current medical condition.

9.1.1.2 Extension of Screening Period Window

A subject may have the Screening Period window extended by 2 weeks for the following reasons:

- Repetition of the Screening Period assessments (Section 9.1.1.1),
- Unexpected operational or logistic delays, or

If more than 42 days have elapsed from screening before first dose of study drug, all screening assessments need to be repeated.

9.1.1.3 Rescreening

Individuals who do not meet the eligibility criteria for participation upon initial screening can be rescreened up to 3 times. All screening tests should be repeated to determine eligibility except for *APOL1* genotyping, confirmation of biopsy-proven APOL1-mediated FSGS by the eligibility review process (Section 9.3.6), and follicle-stimulating hormone (FSH).

Rescreened participants will keep the same subject identification number assigned during the initial screening process. The rescreening period will start from the date of the first assessment of the rescreen. Rescreening assessments may be done in the clinic or using home health. If home health is used for rescreening, abbreviated PE may be done.

9.1.2 Part A

9.1.2.1 Treatment Period

Subjects will be enrolled in Cohort 1 and optional Cohort 2. Treatment Period assessments are listed in Table 3-2. During Treatment Period 1, subjects will receive VX-147 at a dosage

of 15 mg qd for 2 weeks. During Treatment Period 2, subjects will receive VX-147 at a dosage of 45 mg qd for 11 weeks. Dosing details are in Section 9.6.

9.1.2.2 Safety Follow-up

Subjects will have a SFUV 28 (\pm 7) days after the last dose of study drug. SFUV assessments are listed in Table 3-3.

9.1.2.3 Early Termination of Treatment or Early Discontinuation

If a subject prematurely discontinues study treatment, an Early Termination of Treatment (ETT) Visit should be scheduled as soon as possible after the subject decides to terminate study treatment. Subjects who prematurely discontinue treatment will also be required to complete the SFUV, approximately $28 (\pm 7)$ days after their last dose of study drug. The assessments performed at the SFUV are listed in Table 3-3.

If the ETT Visit occurs 3 weeks or later following the last dose of study drug, then the ETT Visit will replace the SFUV, and a separate SFUV will not be required.

After the ETT Visit, subjects will not complete further Part A Visits; these subjects will not continue to Part B.

If a subject withdraws consent for the study, no further assessments will be performed. Vertex may retain and continue to use any data and samples collected before such withdrawal of consent.

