Event/ Assessment ^a	Window: Day 1 (±0 days)	Window: Day 8 (±1 day)	Window: Day 15 (±2 days)	Window: Day 22 (±2 days)	Window: Day 36 (±2 days)	Window: Day 64 (±2 days)	Window: Day 92 (-2 days)		Comments
Abbreviated Physical examination	X	X	Х	X	X	X	Х	X	In addition to the scheduled visits, symptom-directed physical examinations will occur at any time during the study if triggered by AEs or if deemed necessary by the investigator (Section 11.6.3).
Serum chemistry	X Fasted	X	X	X Fasted	X	X	X Fasted	X Fasted	A blood sample will be collected predose after an overnight fast on indicated days. All other days do not require fasting. (Section 11.6.2).
Hematology	X	X	X	X	X	X	X	X	A blood sample will be collected (Section 11.6.2).
Coagulation	X	X	X	X	X	X	X	X	A blood sample will be collected (Section 11.6.2).
Biomarker blood sample	X	X	X	X	X	X	X	X	Section 11.5.1.
VX-147 PK blood sample	intensive	predose	intensive	predose	intensive	predose	X	X	A blood sample will be collected (Section 11.2.1). Intensive PK sampling Day 1, Day 15, Week 5: predose (within 60 min before dosing) and 0.25, 0.5, 1, 2, 4 and 12 hours postdose Post treatment samples (Week 13 and ETT): A single sample collected anytime during the Visit.

Protocol VX19-147-101, Version 6.0

Table 3-2 Study VX19-147-101: Part A Treatment Period 1, Treatment Period 2, and Early Termination of Treatment Visit

	Treatmen	t Period 1 Treatment Period 2					 		
	Day 1 Visit	Week 1 Visit	Day 15 Visit	Week 3 Visit	Week 5 Visit	Week 9 Visit	Week 13 Visit	Early	
Event/ Assessment ^a	Window: Day 1 (±0 days)	Window: Day 8 (±1 day)	Window: Day 15 (±2 days)	Window: Day 22 (±2 days)	Window: Day 36 (±2 days)	Window: Day 64 (±2 days)	Window: Day 92 (-2 days)	Termination of Treatment Visit ^b	Comments
Urine sample β-hCG (urine)	Х°	X	X	X	X (3 samples)	X (3 samples)	X (3 samples)	X	The first morning urine void (predose) will be collected and used for efficacy, safety, and biomarker analyses (Sections 11.3 and 11.6.2). During Week 5, Week 9, and Week 13, 3 samples will be collected on 3 separate days within a 7-day period. If the subject forgets to collect the first morning void on the day of the visit, they may provide this sample predose on a different day within the visit window. Refer to sample handling guidelines to ensure samples are submitted appropriately for analysis. All female subjects of childbearing potential

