9.2.1 Replacement Subjects

Subjects may be replaced at the discretion of Vertex.

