9.9 Removal of Subjects

Subjects may withdraw from the study at any time at their own request. Subjects may be withdrawn from study drug treatment at any time at the discretion of the investigator or Vertex

for safety, behavior, noncompliance with study procedures, or administrative reasons. A subject who withdraws from study drug treatment will continue to be followed unless the subject withdraws consent.

Subjects who discontinue study treatment early should complete the ETT and SFUV, as noted in Sections 9.1.2.2 and 9.1.2.3.

If a subject does not return for a scheduled visit, reasonable effort will be made to contact the subject. In any circumstance, reasonable effort will be made to document subject outcome. The investigator will inquire about the reason for withdrawal, request that the subject return all unused investigational product(s), request that the subject return for a SFUV, if applicable (see Section 9.1.2.3), and follow up with the subject regarding any unresolved AEs.

If a subject withdraws consent for the study, no further assessments will be performed. Vertex may retain and continue using the study data and samples after the study ends and may use the samples and information in the development of the study compound, for other drugs and diagnostics, in publications and presentations, and for education purposes. If a subject withdraws from the study, the study data and samples collected will remain part of the study. A subject will not be able to request the withdrawal of his/her information from the study data. A subject may request destruction of the samples collected from him/her during the study as long as those samples can be identified as his/her samples.

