9.10 Replacement of Subjects

Subjects who withdraw or are withdrawn for nonsafety reasons during the study drug treatment period(s) may be replaced at Vertex's discretion.

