10.6 Compliance

To ensure treatment compliance, the investigator or designee will supervise all study drug dosing that occurs at the site or in the subject's home at required study visits. At each visit, site personnel/home health care nurses will review that the subject is compliant with study drug dosing and remind the subject of study drug dosing requirements. Compliance will also be assessed by ongoing study drug count.

If a subject demonstrates continued noncompliance of study drug dosing despite educational efforts, the investigator should consider discontinuing the subject from the study

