Incomplete or missing data will not be imputed, unless specified otherwise.

Outliers: No formal statistical analyses will be performed to detect and/or remedy the presence of statistical outliers, unless specified otherwise.

Multiplicity: No multiplicity adjustment will be performed.

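### Early stoppers have no scheduled Week 13 UPCR, and the SAP's day-based window drops some of them and admits single, partly off-drug voids from others, with no sensitivity analysis

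*Protocol*

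**What the plan says.** **Follow-up after an early stop.** Protocol Version 6.0, Section 9.1.2.3, requires an ETT visit and an SFUV, then: "After the ETT Visit, subjects will not complete further Part A Visits; these subjects will not continue to Part B". Section 9.9 says "A subject who withdraws from study drug treatment will continue to be followed unless the subject withdraws consent", and its next paragraph adds "Subjects who discontinue study treatment early should complete the ETT and SFUV".

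**Sampling.** Protocol Table 3-2: "During Week 5, Week 9, and Week 13, 3 samples will be collected on 3 separate days within a 7-day period". The urine entries for the ETT visit (Table 3-2) and the SFUV (Table 3-3) show a single sample. Table 3-3 says the SFUV urine is used for efficacy as well as safety.

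**Analysis.** SAP 9.1: "Incomplete or missing data will not be imputed, unless specified otherwise". Protocol 12.3.3.1 leaves sensitivity analyses for treatment or study discontinuation to the SAP. SAP 9.3.1.3 and 9.3.1.4 plan no supportive and no sensitivity analysis, and SAP 3.1 records no departure from the protocol. SAP Appendix A sets the Week 13 UPCR window at (78, 106] in study days, applies it to scheduled and unscheduled visits, and lets one value stand for the visit. Nothing in it requires the subject to be on drug.

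**Replacement.** Protocol 9.2.1: "Subjects may be replaced at the discretion of Vertex". Protocol 9.10: "Subjects who withdraw or are withdrawn for nonsafety reasons during the study drug treatment period(s) may be replaced at Vertex's discretion".

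**The concern.** The primary endpoint is the Week 13 change, and the trial has one open-label arm, so there is no control group in which informative loss could show itself. For a subject who stops early, the calendar decides whether a Week 13 value exists. An early enough stop removes the subject from the primary mean. A later stop can put in one void, possibly weeks off drug, beside completers' averages of up to three. Neither document says this mixture is intended.

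If subjects with less response are more likely to stop and be lost, the reported reduction is too large. Where an off-drug void enters instead, the direction depends on how quickly proteinuria moves after stopping, which is the question Part B is meant to explore.

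Replacement adds to this. The two sections differ on who may be replaced, and neither requires the decision to be made without sight of UPCR. Voids not collected at Week 13 cannot be recovered by later analysis.

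**Working it through.** **1. The plan's own figure.** Protocol 12.1 and SAP 7.2 give SD 0.672 (log scale), n = 10 and an 80% half-width of 0.294. The one-sample t interval gives 1.3830 × 0.672/√10 = 0.2939, which agrees. The primary analysis pools the cohorts (SAP 9.3.1.2), at most about 20 subjects: 1.3277 × 0.672/√20 = 0.1995. With 18 contributing subjects it is 0.211.

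**2. Who gets a Week 13 value.** The window (78, 106] is Days 79 to 106. The SFUV falls 21 to 35 days after the last dose.

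- Latest last dose that cannot reach the window: 79 - 35 = 44, so Day 43 or earlier. A prompt ETT void is also too early. No Week 13 value.
- Latest last dose whose SFUV can still fall inside: 106 - 21 = 85. For last doses on Days 44 to 85 the SFUV void can count as Week 13. It always does for Days 58 (79 - 21) to 71 (106 - 35). At exactly 28 days it does for Days 51 to 78.
- From a last dose of about Day 78, a prompt ETT void also falls in the window.

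The exclusion of non-compliant subjects in SAP 9.3.1.2 does not clearly remove these values. That section sets no cut-off, and the compliance formula in SAP 9.2.5 does not count a permanent stop as an interruption.

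**3. Upper bound for selective loss.** Assume n = 20, SD 0.672, a true geometric mean ratio of 0.70 (-30%), and that the r least-responding subjects are exactly those lost. The expected three largest of 20 standard normal values are 1.8675, 1.4076 and 1.1309. The shift in the mean is -(sum of the top r)/(20 - r) × 0.672.

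| r lost | Shift (log) | 0.70 × exp(shift) | Expected change |
|---|---|---|---|
| 1 | -1.8675/19 × 0.672 = -0.0660 | 0.655 | -34.5% |
| 2 | -3.2751/18 × 0.672 = -0.1223 | 0.619 | -38.1% |
| 3 | -4.4060/17 × 0.672 = -0.1742 | 0.588 | -41.2% |

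The shift at r = 2 is 0.1223/0.1995 = 61% of the pooled half-width.

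**4. Weaker association.** If the correlation between the tendency to stop and Week 13 response is 0.5 (assumed), the shifts halve to -0.033, -0.061 and -0.087, giving about -32%, -34% and -36%. At zero correlation the bias is zero.

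**5. A no-change assumption.** If completers average -30% and 2 of 20 stoppers would have shown no change, the all-subject value is exp(0.9 × ln 0.70) - 1 = -27.5%.

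The documents give no expected dropout, so r is an assumed range throughout.

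**The case against.** The rule is deliberate. Version 2.0 introduced it and narrowed the Week 13 visit window so that primary samples are taken on treatment. In a Phase 2a estimation study, off-drug UPCR answers a different question. That is a fair reason to keep an on-treatment primary. However, the SAP does not deliver one, because its window admits off-drug voids.

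Several stronger readings are tempting, and the documents do not support them:

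- **Rival follow-up schedules.** A reader might set 9.9 against 9.1.2.3. Section 9.9 itself goes on to name only the ETT visit and SFUV, so this is loose wording. Section 10.6 says only that "the investigator should consider discontinuing the subject from the study" after continued non-compliance, and it sets no schedule.
- **A completers-only result.** This follows only for stops up to about Day 43; later stoppers can be counted.
- **No data on stoppers.** They keep UPCR from each visit reached, plus the ETT visit and SFUV. UPCR by visit and a listing of discontinuations are planned. A sensitivity analysis is possible without a measured Week 13 value.
- **Replacement hides the loss.** Replacement is discretionary, Cohort 1 is capped at 10 with no minimum, and nothing removes a replaced subject from the FAS.
- **Bias at n = 10 with perfect selection.** The primary pools the cohorts, and stopping precedes Week 13, so it is unlikely to pick out exactly the worst Week 13 responders.

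**Conclusion.** The point stands as a gap in the plan that should be closed. No Week 13 UPCR is scheduled after an early stop, the promised sensitivity analysis is absent, and Appendix A makes the primary mean an unplanned mix of completers and single, partly off-drug values determined by stopping date. The replacement sections are inconsistent with each other.

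The size cannot be fixed from the documents. Under the stated assumptions, one to three lost subjects out of 20 turn a true -30% into at most -34.5% to -41.2%, into about -32% to -36% at correlation 0.5, and leave it unchanged if stopping is unrelated to response. These figures describe subjects lost from the mean, not those who enter with an off-drug void.

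**What to change.** 1. Unless consent is withdrawn, collect the three home first-morning voids at the planned Week 13 time from subjects who have stopped drug. Flag them as off drug, with days since last dose.
2. Amend Appendix A so that flagged off-drug values, including off-drug ETT and SFUV voids, cannot form the on-treatment primary Week 13 value. Item 1 must not be adopted without this. Voids on Days 86 to 92 lie inside (78, 106], and note 5 selects the 7-day cluster with the most values, so three off-drug voids would otherwise become that subject's primary value.
3. Add the promised sensitivity analysis as one supportive FAS summary of Week 13 UPCR regardless of stopping, using the values from item 1. Set stoppers who lack a value first to their last on-treatment UPCR, then to no change.
4. Reconcile 9.2.1 with 9.10, and the follow-up wording of 9.9 with 9.1.2.3. Make replacement decisions without reference to UPCR. Report the number replaced, with their last on-treatment UPCR, beside the primary result.

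The cost is a protocol and SAP amendment, a few extra urine kits and minor subject burden. Home visits are already permitted, and no new assay is needed. The supportive estimate may be less favourable than the primary.
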